## Missing data

Patients with missing outcome data will be excluded from the analyses for that outcome exposure. Exposure data (study hospital and study phase) is expected to be 100% non-missing. Data is also expected to be 100% non-missing for all eligible encounters for covariates for primary/secondary outcome multivariable models. However, if this is not the case for primary and secondary outcome analyses, we will apply the following approaches based on multiple imputation using chained equations (10 datasets, results combined using Rubin's rules):

- 100% of eligible encounters with complete data: perform complete case analysis.
- ≥95% of eligible encounters with complete data: perform complete case analysis for the main outcome reporting/interpretation multivariable analysis; use multiple imputed data as a sensitivity analysis.
- <95% of eligible encounters with complete data: use multiple imputed data for the main outcome reporting/interpretation multivariable analysis; perform complete case analysis as a sensitivity analysis.

For safety outcomes, there is expected to be missingness for some prespecified covariates for patients included in "all ED" and "sepsis mimic" cohorts.

- 100% of eligible encounters with complete data: perform complete case analysis.
- ≥95% of eligible encounters with complete data: perform complete case analysis for the main outcome reporting/interpretation multivariable analysis; use multiple imputed data as a sensitivity analysis.
- <95% of eligible encounters with complete data: use multiply imputed data for the main outcome reporting/interpretation multivariable analysis; perform complete case analysis as a sensitivity analysis.

Where performed, multiple imputation models will be performed separately for primary/secondary vs safety outcomes. Variables included in the model will include each outcome (within the outcome class), study site, study phase, all covariates (within the outcome class), and additional potentially-informative variables identified based on expert opinion and literature review. We will use predictive mean matching using five nearest neighbors for imputation of continuous variables and logistic regression with bootstrap for binary variables.

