### Data analysis

Analyses for causal inference regarding primary, secondary and safety outcomes will employ a quasi-experimental method called *difference-in-difference* (DID) analysis to control for secular trends and confounding of unknown individual factors associated with the outcome of interest. The DID approach will provide an estimate of the effect of the Code Sepsis intervention on primary, secondary, and safety outcomes by comparing the intervention and control hospitals during the pre- and post-implementation periods (Figure 1).

For the primary outcome, DID analysis will use multivariable linear regression to compare the adjusted mean door-to-

antibiotic time (primary outcome) at the intervention hospital

pre- versus post-implementation of the Code Sepsis protocol using the measured change at contemporaneous control non-intervention hospitals to control for pre-/post-intervention changes not attributable to protocol implementation after adjustment for potential confounders.

The following equation will be used to estimate the adjusted mean differential change in the primary outcome, door to antibiotic time:

$$Y_{igt} = \beta_0 + \beta_1 Int_g + \beta_2 Post_t + \beta_3 (Int_g * Post_t) + \beta_4 Cov$$

Where  $Y_{igt}$  is the door-to-antibiotic time for patient *i* treated at an intervention or non-intervention ED *g* at pre- or post-intervention time *t*. *Int* is a binary indicator for the subject being treated at an intervention hospital; *Post* is a binary indicator the post-intervention period; and *Cov* represents a vector of patient-level covariates. The  $\beta_3$  parameter from the regression model presented above estimates the adjusted mean differential change in door-to-antibiotic time observed in the Code Sepsis intervention hospital compared to the control hospital. We will consider the Code Sepsis intervention to have had an impact if  $\beta_3$  is statistically significant and different from zero.

The parallel trend assumption will be tested using the approach outlined by Callaway and Sant'Anna. This approach allows for testing the parallel trend assumption after conditioning on covariates. This approach is

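### The imputation model names study site and study phase but not their interaction, which is the difference-in-differences effect; coded as listed, it can bias the safety estimates for common outcomes in the all-ED cohort.

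*SAP*

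**What the plan says.** Under Data analysis, the SAP sets the same estimand for all three outcome classes: "The DID approach will provide an estimate of the effect of the Code Sepsis intervention on primary, secondary, and safety outcomes". In the model equation that effect is the coefficient on the product of the intervention-site and post-period indicators.

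Under Missing data, it specifies "multiple imputation using chained equations (10 datasets, results combined using Rubin's rules"). The content of the imputation model is given as a list: "Variables included in the model will include each outcome (within the outcome class), study site, study phase, all covariates (within the outcome class"), followed by "additional potentially-informative variables identified based on expert opinion and literature review". No product of site and phase is named, no imputation within the four site-by-phase groups is mentioned, and no functional form is given.

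The same section says where imputation is likely to be used:

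- Covariates for primary and secondary outcomes are expected to be fully observed. By contrast, "For safety outcomes, there is expected to be missingness for some prespecified covariates" in the all-ED and sepsis-mimic cohorts. The fraction is not stated.
- At 95% completeness or above, the rule is to "perform complete case analysis for the main outcome reporting/interpretation multivariable analysis; use multiple imputed data as a sensitivity analysis".
- Below 95%, for safety outcomes, it is to "use multiply imputed data for the main outcome reporting/interpretation multivariable analysis; perform complete case analysis as a sensitivity analysis".
- "Patients with missing outcome data will be excluded from the analyses for that outcome exposure", so only covariate values are imputed for analysis.

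**The concern.** An imputation model should be at least as rich as the analysis model it feeds. Here the analysis model contains site × phase and the imputation model, as listed, does not. The imputed part of a covariate then cannot show its own site-by-phase change, except so far as the outcome or other imputation variables carry it.

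That change is the confounding which covariate adjustment is meant to remove. Suppose patients at the intervention ED became sicker after February 2020 relative to the control EDs. Fully observed severity would absorb the resulting rise in antibiotic use. Severity imputed without the interaction absorbs only part of it, and the rest goes to the DID coefficient.

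At stake is chiefly the all-ED antibiotic-use comparison, which bears on the protocol's hypothesis (section 3.2) that treatment is faster without more overtreatment. That cohort is large, so a modest bias is not hidden by sampling error.

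**Working it through.** **The plan's own figures.** The documents give no missing fraction, imputation bias or safety standard error to reproduce. The one design figure (90% power for 16 minutes) concerns the primary outcome and is not used here.

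**Approximate size of the bias.** Let the covariate's log-odds slope be b per SD, the missing fraction m, and its extra shift in the intervention-post group d (in SD). If imputed values carry none of that shift, then

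bias in the DID log-odds ≈ b × m × d.

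For b = 1.0, m = 0.4 and d = 0.2 this is 1.0 × 0.4 × 0.2 = 0.08. For b = 0.5 and m = 0.2 it is 0.5 × 0.2 × 0.2 = 0.02. Simulated values should be somewhat lower, because the outcome is in the imputation model and carries part of the shift.

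**Simulation 1: missing completely at random.** Logistic DID, 40,000 encounters, one incomplete covariate, predictive mean matching with five neighbours, 20 replicates, 5 imputations (the SAP plans 10). Bias is measured against the full-data fit. Ranges cover slopes 0.5 to 1.0.

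| True log-OR | Shift | Missing | Without site × phase | With site × phase |
|---|---|---|---|---|
| 0 | 0 | 5–40% | at most 0.007 in size | at most 0.007 in size |
| 0 | 0.2 SD | 5% | +0.005 to +0.008 | about 0 |
| 0 | 0.2 SD | 20% | +0.018 to +0.031 | −0.003 to −0.002 |
| 0 | 0.2 SD | 40% | +0.036 to +0.070 | −0.002 to +0.005 |
| 0.3 | 0 | 20% | −0.011 to −0.004 | −0.004 to −0.001 |
| 0.3 | 0 | 40% | −0.020 to −0.006 | −0.002 to 0.000 |

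The 0.08 and 0.02 approximations correspond to simulated values of 0.070 and 0.018. The largest attenuation of a true effect is 0.020/0.3, about 7%.

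**Simulation 2: missingness depends on treatment.** 80,000 encounters, true effect 0, about 14% treated, slope 0.9, covariate missing in 5% of treated patients and in the stated share of untreated patients.

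| Shift | Missing in untreated | Without | With |
|---|---|---|---|
| 0.1 SD | 10% | +0.007 | 0.000 |
| 0.1 SD | 20% | +0.013 | −0.002 |
| 0.1 SD | 40% | +0.026 | −0.004 |
| 0.2 SD | 20% | +0.028 | 0.000 |
| 0.2 SD | 40% | +0.054 | −0.001 |

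With no shift there was no bias under either model.

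**Comparison with the standard error.** Protocol Table 1 gives 89,000 annual visits at the intervention ED and 49,000 + 65,000 = 114,000 at the control EDs. With two one-year phases and outcome proportion p,

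SE = √[(2/89,000 + 2/114,000) / (p(1 − p))].

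- Antibiotic use, assumed p = 0.14: √(0.0000400/0.1204) = 0.018. With half the visits, 0.018 × √2 ≈ 0.026.
- Adverse event, assumed p = 0.01: √(0.0000400/0.0099) = 0.064.
- Mimic cohort, assumed 1% of visits with p = 0.20: √(0.00400/0.16) = 0.16.

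A bias of 0.026 is therefore 1.4 SE for antibiotic use at full volume (0.026/0.018) and 1.0 SE at half volume, but 0.4 SE for the rare event and under 0.2 SE for the mimic cohort. Using P(|Z + bias/SE| > 1.96), a nominal 5% error becomes roughly 30%, 17%, 7% and 5% respectively. These rates ignore the extra variance from multiple imputation.

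**The case against.** - **The list gives variables, not a functional form.** A reader might infer that the SAP rules the interaction out. It does not: the term is unstated, and the list is open-ended. What stands is that a programmer following it literally would enter site and phase additively.
- **The bias is conditional.** With no true effect it needs a differential shift that the other imputation variables do not explain. The simulations above use a single incomplete covariate, whereas the SAP's model also holds age, sex, comorbidity, insurance, temperature, blood pressure and the safety outcomes. In a rerun of the 0.1 SD, 40% case with a fully observed covariate correlated 0.5 with severity, bias fell from +0.027 to +0.011 when that covariate carried half the shift, and to +0.001 when it carried all of it. This stands, and it makes the tabulated values high for a rich imputation model.
- **The inputs are assumed.** The documents give no missing fraction, slope, shift or antibiotic-use rate. The full-volume SE is a floor, because the all-ED cohort drops children, trauma, recent antibiotics, unevaluated patients and repeat visits. A reader might infer that false safety signals are likely, or that every safety outcome is exposed; neither is supported.
- **The plan has safeguards.** Imputation leads only below 95% completeness, complete-case results are then reported beside it, and safety findings are labelled hypothesis generating. This limits the consequence. It does not settle which model the main safety estimate should use.

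**Conclusion.** The concern holds as a gap in specification with a conditional effect. The SAP does not state that the imputation model contains the DID term. Coded as listed, it can bias the safety DID, in either direction according to the sign of the differential covariate shift, or slightly attenuate a true effect.

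For slopes of 0.5 to 1.0 per SD and shifts of 0.1 to 0.2 SD, the bias is about 0.01 or less at 5% missing, 0.013 to 0.03 at 20%, and 0.026 to 0.07 at 40%. Including the interaction essentially removes it. Against an SE of 0.018 or more, it could matter for common outcomes in the all-ED cohort, chiefly antibiotic use. It is small for rare adverse events and for the mimic cohort.

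A reader might extend this to the primary result or to the heterogeneity models. The documents do not support that: heterogeneity is specified only for the primary outcome, whose covariates are expected to be complete.

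**What to change.** Add to the SAP's Missing data section: *Each imputation model will include the study site × study phase interaction.* Imputing separately within the four site-by-phase groups can be allowed as an alternative, but only in the large all-ED cohort. In the smaller cohorts the product term is the safer choice.

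The cost is one sentence and one extra term in the imputation code. No new data are needed, and the rest of the missing-data rules can stay as they are.

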### Power

It was estimated that the intervention ED provides care for 1,650 sepsis patients annually (approximately 4.5 sepsis patients per day) and the control EDs together care for a total of 2,200 sepsis patients annually (approximately 6 sepsis patients per day). Estimated control door-to-antibiotic time for ED sepsis patients was an average 170 (±75) minutes based on 2013-2017 data from study hospitals, with approximately 5-10% of patients receiving antibiotics within 1 hour of ED arrival. Based on these assumptions, we estimated 90% power to detect a difference-in-differences change of 16 minutes or more in door-to-antibiotic time associated with Code Sepsis implementation, with the measurement population being all ED sepsis patients. Power calculations employed Monte Carlo simulations.

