#### 7.3 Sample size/power analysis

Using 2013 to 2017 data from our study hospitals, we estimated conservatively that the intervention ED provides care for 1,650 sepsis patients annually (approximately 4.5 sepsis patients per day) and the

control EDs together care for a total of 2,200 sepsis patients annually (approximately 6 sepsis patients per day). Based on the design and our pilot testing of the Code Sepsis protocol, a very conservative estimate of door-to-antibiotic time for patients who receive antibiotics after evaluation under the Code Sepsis protocol is 50 minutes. By comparison, our preliminary data from 2013 to 2017 indicates current mean (SD) door-to-antibiotic time for ED sepsis patients is 170 (±75) minutes and that only 5% of patients currently receive antibiotics within 1 hour of ED arrival. Assuming (again conservatively) that the Code Sepsis protocol is activated for 30% of sepsis patients treated in the intervention ED during the full implementation phase (study phase #3), we will have 90% power to detect a difference-in-differences change of 16 minutes or more in door-to-antibiotic time associated with Code Sepsis implementation, with the measurement population being all ED sepsis patients. Power calculations employed Monte Carlo simulations, for which technical details are available upon request.

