# Inclusion/exclusion criteria

Cohort	Inclusion	Exclusion	Cohort eligibility indicator variable*
ED sepsis cohort (primary analysis cohort)	
 
(1) Age ≥18 years
 
(2) Arrival to an intervention or control ED during study period
 
(3) Met all Sepsis-3 criteria in the ED
 
Acute organ failure in the ED defined by SOFA score while in the ED ,≥2 points above baseline
 
Suspected or confirmed infection while in the ED, based on having both: 
 
i. Administration of ,≥1 IV or IV-equivalent antibiotics while in the ED for suspected infection (i.e. antibiotics not given for prophylaxis)
 
ii. Collection of ,≥1 body fluid cultures while in the ED
 
 
 
	
 
Trauma patient
 
Subsequent eligible ED visit with sepsis after first eligible encounter during an analysis window
 
	cohort_sepsis
All adult ED patients cohort	
 
(1) Age ≥18 years
 
(2) Arrival to an intervention or control ED during study period
 
	
 
Trauma patient
 
Received antibiotics within 6 hours prior to study ED arrival
 
Subsequent eligible ED visit after first eligible encounter during an analysis window
 
Left ED without evaluation or treatment
 
	cohort_all
Sepsis high-risk cohort	
 
Age ≥18 years
 
Arrival to an intervention or control ED during study period
 
First recorded temperature ≥38.0°C
 
First-recorded vital sign data meets ≥2 of:         
 
a. Systolic blood pressure <90 mmHg
 
b. Glasgow Coma Scale (GCS) score <15
 
c. Respiratory rate ≥22 breaths/min or oxygen saturation <85%
 
 
 
	
 
Trauma patient
 
Received antibiotics within 6 hours prior to study ED arrival
 
Subsequent eligible ED visit after first eligible encounter during an analysis window
 
Left ED without evaluation or treatment
 
	cohort_risk

Cohort	Inclusion	Exclusion	Cohort eligibility indicator variable*
Sepsis	(1) Age ≥18 years	(1) Trauma patient	cohort_mimics
mimic	(2) Arrival to an intervention or control ED during study period	(2) Received antibiotics	

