limited in that it only considers the control and treated groups during the pre-implementation phase. If the pre-test of parallel trends assumption fails, then we will weight the gamma regression model with propensity scores. As demonstrated by Stuart *et. al*, this will balance the covariates amongst the four study groups defined by their treatment status as well as time (pre vs post). We will leverage the covariate balancing propensity score (CBPS) library in R to generate propensity scores. This weighting approach can recover treatment effects in that it allows for adjustments due to observed baseline covariates that differ either across groups or over time. Covariates that will be used in generating propensity scores will include age; sex; weighted Elixhauser comorbidity score; English language preference; first-available heart rate, temperature, systolic blood pressure, and respiratory rate; acute physiology score; ED arrival at nightime (10 pm to 6:59 am), ED arrival on weekend (midnight Saturday to 11:59 pm Sunday), SARS-CoV-2 test result (positive, negative, or not performed during ED-associated hospitalization or within 14 days preceding ED arrival); and insurance type. For analyses involving a cohort of patients with sepsis, propensity score covariates will additionally include arrival to ED via ambulance; presentation from a long term care facility; serum lactic acid level checked and ≥2 mmol/dL; ED SOFA score; and ED-diagnosed infection source.

In order to account for the right skew known to exist in door-to-antibiotic time we will use generalized linear gamma regression to estimate the DID. Evaluation of secondary outcomes will employ an analogous approach using multivariable linear, Poisson, logistic, or gamma regression as appropriate. Data from the wash-in phase will be excluded from DID analyses. All multivariable models will be adjusted for demographic and clinical parameters with known or plausible associations with both outcomes and treatment hospital, presentation before or after Code Sepsis implementation, and/or Code Sepsis activation as well as select precision variables as detailed below. Analyses for secondary, safety, and heterogeneity of treatment effect outcomes will not be adjusted for multiple comparisons and will therefore be considered hypothesis generating.

Statistical significance will be set to p < 0.05. All analyses will be conducted with R.

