#### Sensitivity analyses

*Key sensitivity analysis*: To augment causal inference from the primary analysis and evaluate for the possibility of non-parallel trends in the primary outcome at intervention versus control hospitals during the preintervention phase, we will perform a sensitivity analysis evaluating the adjusted primary outcome (door-toantibiotic time) with a multi-group interrupted time series analysis. The following segmented regression suggested by Ryan et.al. will be used to estimate the effect of the Code Sepsis intervention on door-toantibiotic time:

$$Y_{igt} = \beta_0 + \beta_1 Time + \beta_2 (Time * Int_g) + \beta_3 Post_t + \beta_4 (Int_g * Post_t) + \beta_5 Cov$$

Where  $Y_{igt}$  is the door-to-antibiotic time for patient *i* treated at an intervention or non-intervention ED *g* at pre- or post-intervention time *t*. *Time* is a continuous variable indicating the bi-weekly count from the start of the observation period; *Int* is a binary indicator for the subject being treated at an intervention hospital; *Post* is a binary indicator for the post intervention period. The  $\beta_4$  parameter from the regression model is interpreted in nearly the same manner as the primary outcome, in that it estimates the adjusted differential change in door-to-antibiotic time between the control and CodeSepsis hospitals. This model allows for the trends to differ between the intervention and control hospitals during the pre-intervention phase. We will consider the Code Sepsis intervention of have had an impact if  $\beta_4$  is statistically significant and different from zero.

In order to account for the right skew known to exist in door-to-antibiotic time we will use generalized linear gamma regression to estimate the DID. Data from the wash-in phase will be excluded from the sensitivity analysis.

- Other primary outcome sensitivity analyses:
  - Repeat primary analysis among patients in "sepsis high-risk" cohort who received antibiotics in the ED.
  - Repeat primary analysis in the dataset comprising all *encounters* (≥1 encounter per patient) meeting sepsis criteria between ED arrival and ED departure, using generalized linear models with a random effect for patient to account for non-independence.
  - $\circ$   $\,$  Missing data sensitivity analyses as described in the "Missing Data" section  $\,$

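### The SAP's 90% power at 16 minutes does not follow from its stated inputs (they give 99.6%, or 90% at 11.2 minutes), and a significant β3 assumes no ED-specific shift between phases

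*SAP*

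**What the plan says.** **Power.** SAP, Power: "Based on these assumptions, we estimated 90% power to detect a difference-in-differences change of 16 minutes or more in door-to-antibiotic time". The assumptions referred to are 1,650 sepsis patients a year at the intervention ED, 2,200 a year at the two control EDs combined, and a mean of 170 (SD 75) minutes. Protocol 7.3 gives the same result and adds that 30% of intervention-ED sepsis patients would be activated and that treatment under the protocol would take 50 minutes. It ends: "Power calculations employed Monte Carlo simulations, for which technical details are available upon request". Neither document gives the per-phase counts, the data model or any variance component used in the simulation.

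**Phases.** The SAP's table of study phases gives two analysis phases of one year each. On the three months between them: "Data from the wash-in phase will be excluded from DID analyses". The sepsis cohort also drops a "Subsequent eligible ED visit with sepsis after first eligible encounter during an analysis window".

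**Model and decision rule.** The SAP's primary model has Int, Post, Int*Post and patient-level covariates. Int "is a binary indicator for the subject being treated at an intervention hospital", so the two control EDs share one level. "We will consider the Code Sepsis intervention to have had an impact if" is completed by the condition that β3 is significant and non-zero, at p < 0.05.

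**Safeguards.** The SAP tests parallel trends and says of that test that "it only considers the control and treated groups during the pre-implementation phase". Propensity weighting follows if the test fails. The key sensitivity analysis is an interrupted time series: "This model allows for the trends to differ between the intervention and control hospitals during the pre-intervention phase". The only random effect in the plan is for patient, in one sensitivity analysis.

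**The concern.** The power paragraph presents its result as a consequence of the inputs printed beside it, but those inputs give a detectable difference about 30% smaller. A reader cannot reproduce the design's power or tell whether the simulation already allowed for variation between EDs. That matters because the explanations call for different corrections: a slip in the counts, an unstated SD, or a deliberate ED-level allowance.

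The second issue is how β3 is read. With one intervention ED, any change peculiar to that ED between the phases enters β3 in full, and nothing in its standard error reflects this. The setting makes such a change possible. The control EDs are regional referral sites staffed by other physician groups, the post phase starts in February 2020, and SARS-CoV-2 test result appears only among the covariates for the contingent weighting. At stake is a small effect being declared an impact, or being overstated.

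**Working it through.** **1. The plan's own figure.** Inputs: 1,650 and 2,200 per phase (annual counts, one-year phases), SD 75, alpha 0.05. The test is taken as two-sided because the rule asks for a β3 different from zero. Patients are assumed independent.

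- SE = 75 × √(2/1650 + 2/2200) = 3.454 minutes
- Power at 16 = Φ(16/3.454 − 1.960) = Φ(2.672) = 99.6%
- Difference at 90% power = (1.960 + 1.2816) × 3.454 = 11.2 minutes

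The printed 90% at 16 minutes is not reproduced.

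**2. Variants of the stated inputs.**

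- 4.5 and 6 patients a day: 99.6%. One-sided 0.05: 99.9%.
- Gamma model (log link assumed, since the SAP names none): SE = (75/170) × √(2/1650 + 2/2200) = 0.0203; log(154/170) = −0.0988; power = Φ(4.86 − 1.96) = 99.8%. Simulated gamma data (mean 170, SD 75, 4,000 runs) gave 99.7%. Right skew does not close the gap.
- 30% of intervention patients carrying the whole effect, with a mean effect of 16 minutes: gain per activated patient 16/0.30 = 53.3; post-phase SD = √(75² + 0.3 × 0.7 × 53.3²) = 78.9; SE = √(75²/1650 + 78.9²/1650 + 2 × 75²/2200) = 3.506; power 99.5%; 90% power at 11.4 minutes.

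**3. What would give 16 minutes.** The SE needed is 16/3.2415 = 4.936, a variance ratio of (4.936/3.454)² = 2.04. Three unstated inputs would supply it:

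- annual counts split over the two phases (825 and 1,100): SE 4.885, power 90.6%, or 89.7% with the mixture above;
- an SD of about 107;
- an independent shift in each ED-by-phase mean with SD √((4.936² − 3.454²)/3) = 2.04 minutes.

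The first-visit rule would have to remove 1 − 1/2.04 = 51% of patients.

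**4. β3 under ED-level shifts (illustrative; the documents give no ED-level SD).** Let s be the SD of an independent shift, with two control EDs of equal size. If s applies to each ED-by-phase cell, the added variance is 2s² + 2s²/2 = 3s². If s is the SD of each ED's pre-to-post change, it is s² + s²/2 = 1.5s². Type I error at nominal 5% is 2[1 − Φ(1.96 × 3.454/√(3.454² + k s²))], with k = 3 or 1.5:

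| Assumed s (minutes) | per cell | of the change |
|---|---|---|
| 1 | 8% | 6.5% |
| 2 | 17% | 11% |
| 3 | 28% | 18% |
| 5 | 47% | 34% |

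The planned safeguards do not cover this case. The trend test uses pre-phase data only. The weights balance observed covariates, and only if that test fails. In the time-series model an abrupt ED-specific step loads on Int*Post, the coefficient of interest.

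**5. Sensitivity of a control-versus-control DID.** With 1,100 patients per control ED per phase (assumed), SE = 75 × √(4/1100) = 4.52. It would be significant only 24% or 42% of the time for s = 3 or 5 per cell (15% or 29% if s is the SD of the change).

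**6. Cohort count.** At the power-section rates, phases 1 and 3 give 2 × (1,650 + 2,200) = 7,700. Protocol 9.2.3 gives about 9,450 for the primary analysis cohort.

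**The case against.** The discrepancy is in the safe direction. All eligible patients in fixed calendar windows are included, so no sample size or phase length depends on the 16 minutes. The protocol calls its inputs conservative and offers the simulation details on request. The study is Phase 2a, and the SAP names parallel trends as an assumption, tests it, admits the test's limit and adds a time-series analysis. Few-group DID always has this weakness.

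Most of that stands. It keeps the power point to a correction, and it limits the β3 point to a caveat, a cheap model change and an optional check. It does not rescue the printed figure: the conservative inputs are already in the calculation, and details held elsewhere are not in the plan.

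Four stronger readings are tempting and unsupported.

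- *The trial is underpowered.* The stated inputs imply more power than printed, and the protocol's own figures imply an effect of 0.30 × (170 − 50) = 36 minutes. Equally, no power can be guaranteed at 36 minutes if EDs do shift, because the ED-level SD is unknown and three EDs cannot estimate it reliably.
- *The primary test has a false-positive rate of 17% or 47%.* Those rates follow from assumed SDs. The documents show only that the nominal 5% is conditional.
- *The 30% mixture with its full 120-minute gain supplies the missing variance.* That mixture belongs to a 36-minute effect and cannot be paired with a 16-minute one.
- *The 9,450 is a mislabelled 27-month count.* That needs 4,200 patients a year, a rate in neither document. The stated 3,850 gives 3,850 × 27/12 = 8,663, while 10.5 a day over 900 days also gives 9,450. Its basis is undocumented.

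**Conclusion.** The power statement is wrong as written. Under independence, one-year phases and two-sided alpha 0.05, the stated inputs give 99.6% power at 16 minutes and 90% at 11.2 minutes (99.5% and 11.4 with a coherent 30% mixture). The arithmetic is firm; which unstated input produced 16 minutes cannot be known from the documents.

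The β3 point is a real but conditional limit. Its p-value is valid only if no ED shifted between phases for reasons of its own, which one intervention and two control EDs cannot separate from the intervention. Its size is undocumented. The point should be fixed because the correction is cheap, not because the design fails.

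**What to change.** 1. **Power statement.** State the simulation's patients per ED group per phase, SD, alpha, treated fraction and any ED-level variance. If it used full annual counts per phase and independent patients, restate the result as about 99.6% at 16 minutes, or 90% at about 11 minutes. If it split the counts, correct them and restate. If it included ED-level variance, give the value.
2. **Primary model.** Replace the single Int main effect with hospital fixed effects, keeping Int*Post, so that a changing mix of the two control EDs cannot bias β3. With assumed figures, control EDs 20 minutes apart and a 10-point change in mix move β3 by 0.10 × 20 = 2 minutes. This does not address ED-specific shifts.
3. **Caveat.** State that declaring an impact on p < 0.05 assumes no ED-specific shift between phases. The control-versus-control DID over the same phases may be reported as an optional check, noting its low sensitivity: a null result is not reassurance.
4. **Counts.** The study team should reconcile 9,450 with the roughly 7,700 implied for phases 1 and 3, and give the basis of each.

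The cost is a reworded paragraph, one extra model parameter, one caveat sentence, one reconciled count and, optionally, one analysis of data already held.
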